## VIII. Risks

### VIII.1 *What are the risks to subjects including*

- emotional or psychological
- financial
- legal or social
- physical?

In general, microneedle treatments are well tolerated. However, the skin could become irritated or inflamed from the microneedle insertion or from the adhesives (either on the patches used to apply the microneedles and make measurements, or the medical tape used to hold the occlusive patches in place). There may be mild discomfort, itching, redness, bruising, inflammation, or hyper-/hypopigmentation at the treatment sites or where adhesives were in contact with the skin. Loss of confidentiality is also a risk.

### VIII.2 *What have you done to minimize the risks?*

- *If applicable to this study ALSO include:*
  - *How you (members of your research team at Iowa) will monitor the safety of individual subjects.*
  - *Include a description of the availability of medical or psychological resources that subjects might require as a consequence of participating in this research and how referral will occur if necessary (e.g. availability of emergency medical care, psychological counseling, etc.)*

During the consent process the subjects will be counseled about the micropatch. The skin will be cleansed thoroughly with alcohol wipes prior to applying the micropatch treatments (cleaning technique similar to that used for insertion of a typical hypodermic needle). They will also be counseled about the possibility of local skin irritation and redness from the adhesive tape. Subjects will be closely observed during the measurements and during treatment with the micropatches; emergency facilities and staff will be available if necessary. Subjects will be instructed to contact a member of the study team if problems arise at any time during their participation in the study (all pertinent contact information will be provided to the subjects). Within 3 - 4 days following study completion, a member of the research team will call or email the subject to follow-up and be sure that no irritation or infection has occurred. The risk of loss of confidentiality will be minimized by keeping all documents in a locked cabinet that is only accessible to members of the research team. All electronic forms of data will be kept on a secure-server supported by the University of Iowa that allows only members of the research team access.

### VIII.3 *Does this study have a plan to have an individual or committee review combined data from all subjects on a periodic basis (such as summary or aggregate safety and/or efficacy data)?*

No

## IX. Benefits

### IX.1 *What are the direct benefits to the subject (do not include compensation or hypothesized results)?*

There are no direct benefits to the subjects.

### IX.2 *What are the potential benefits to society in terms of knowledge to be gained as a result of this project?*

Microneedle-assisted drug delivery is a very promising method of administration. It is more tolerable than standard hypodermic needles for injections, and delivery through the skin bypasses many of the shortcomings involved with oral medications. There are several microneedle devices in use around the world, mostly for cosmetic purposes. The first microneedle product cleared by the FDA for influenza vaccine administration is Soluvia, which is marketed by Sanofi as Fluzone Intradermal. As the use for microneedles in drug therapy gains interest, it is very important to understand how therapeutic endpoints will differ with microneedle application at different body sites and in different skin types. The first step in understanding this is to characterize the response to microneedles in various anatomical sites and races. This knowledge is currently lacking, but will be directly related to the micropore closure rate (assessed by impedance), skin hydration, and redness/color data gathered from this study.

## X. Privacy & Confidentiality

### X.1 *What are you doing to protect the privacy interests of the subjects?*

No direct patient identifiers will be recorded on data collection material. Instead, subjects will be assigned a subject number on study materials. Only the data necessary to answer the research question will be collected, and all consent processes and study procedures will take place in a private location in the Clinical Research Unit.

### X.2 *Are you collecting the Social Security Number of any subjects for any purpose?*

Yes

### X.3 *Provide the intended usage of SSN:*

- To provide compensation to subjects

### X.4 *How will information/data be collected and stored for this study (check all that apply):*

- Paper/hard copy records (hard copy surveys, questionnaires, case report forms, pictures, etc.) - Hard copies will only be transported by members of the research team. Hard copies will be stored in the office of the Clinical Coordinator in C44-P of the ICTS center of UIHC or in the office of the Clinical Coordinator in 558 CPB in a locked filing cabinet only accessible to members of the study team.  

- Electronic records (computer files, electronic databases, etc.) - Electronic records (computer files, electronic databases, etc.) - Electronic results and data (after direct patient identifiers have been removed) will be kept on a password protected shared drive (College of Pharmacy, University of Iowa) that only members of the research team will be able to access.
  - Name - [name]
  - Title - IT Director
  - University Job Classification - Faculty/Staff

**X.5** *Do the confidentiality protections indicated above allow only members of the research team to access the data/specimens?*  
Yes

**X.7** *Does your study meet the NIH criteria for a [Certificate of Confidentiality](#) or will you be applying for Certificate of Confidentiality?*  
No

## XI. Data Analysis

**XI.1** *Describe the analysis methods you will use, including, if applicable, the variables you will analyze*  
Descriptive statistics will be used for subject demographics. Each subject will serve as their own control, and paired t-tests will determine differences in TEWL (water loss measurements) and impedance from baseline to post-microneedle insertion. This will be used to determine if the microneedles adequately breached the skin barrier, demonstrated by a significant increase in TEWL from baseline and a significant decrease in impedance from baseline. For the colorimetry, and hydration measurements, each daily measurement will be compared to its baseline at that site, as well as to its hydration control (untreated, occluded site), using paired t-tests.  
Impedance data will be analyzed using similar methods as our previous study, and will ultimately be used to calculate the half-life of micropore closure. Z-pores values will be calculated from impedance measurements taken immediately following and over the days following microneedle treatment. These values will be converted to admittance (the inverse of impedance), which can demonstrate how “open” the micropores are in a very intuitive manner. If a micropore has a maximum admittance, then the micropore is 100% open. Using this information, we will plot admittance vs. time and calculate a rate constant of micropore admittance (k). The rate constant is then used to calculate the half-life of micropore closure, which thus describes a rate of closure in units of time. This micropore half-life will serve as the primary endpoint and will be compared among locations within a group, among groups within a location, and among locations in all groups.

**XI.2** *Provide the rationale or power analysis to support the number of subjects proposed to complete this study.*  
There are no data in any population other than Caucasian individuals and no data directly comparing micropore closure at various anatomical sites to guide a formal power analysis. Our calculation of subject number was based on what is feasible for a pilot study to give enough preliminary data for a power analysis later. We plan to enroll subjects into 5 groups based on self-identified race/ethnicity. Each of the following groups will have 10 subjects each: African American/Black, Hispanic/Latino, Caucasian/White, Asian, and bi-/multiracial. We have selected 70 subjects as the number for enrollment to help account for those who will complete the informed consent but will either be screened out afterwards or will not participate in the study to completion.

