**DESCRIBE:**

- *What subjects will be asked to do/what happens in the study (in sequential order)*
- *The time period over which procedures will occur*
- *The time commitment for the subject for individual visits/procedures*
- *Long-term followup and how it occurs*

Following consent, a member of the study team will obtain the following demographic information directly from the subject: age, height, weight, and gender. A member of the study team will also identify the subject's Fitzpatrick skin type, and obtain a list of current medications and ongoing medical conditions. The subject will be asked to elaborate on the duration and severity of medical conditions and any treatments received. No medical records will be consulted to obtain or confirm this information. A member of the research team will use this information to screen out subjects meeting any of the exclusion criteria defined in VI.13. Subjects who pass the screening may proceed to the next step described below. Consent and screening procedures will take approximately 1 hour.

On Day 0 (may be the same day as consent is obtained), the subject will sit in a study room at the CRU for 30 minutes prior to any procedures. This allows the subject's skin to acclimate to the ambient environment in the study room (temperature, humidity). Following this acclimatization, the researcher will identify and mark with a marker 5 sites at each of the following 3 locations (for a total of 15 sites): upper arm, volar forearm, and abdomen. Hair may be clipped (but not shaved) at the sites if necessary. Noninvasive baseline measurements will be taken at each of the 15 sites as follows:

- Hydration will be measured by gently pushing a corneometer probe against the skin. The measurement will take less than 30 seconds at each site.
- Transepidermal water loss (TEWL) will be measured by resting a probe gently against the skin. This measurement will take 1-3 minutes at each site. (TEWL will only be measured on Day 0.)
- Electrical resistance (impedance) will be measured with an impedance meter by applying gel electrodes to each site and a reference electrode at a nearby site. The measurement will be repeated 3 times at each site, and will take less than 2 minutes total at each site.
- Skin color and redness will be measured by placing a colorimetry probe gently against each site. This measurement will take less than 30 seconds at each site.

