Following baseline measurements on Day 0, micropatches will be applied to three of each set of five sites. The sites will first be cleansed with an alcohol swab. A sterilized micropatch containing 50 tiny projections, each 800 um in length, will be placed perpendicular to the skin, and the researcher will apply gentle pressure to the back of the patch for 10 seconds. The researcher will then remove the patch, rotate it 45 degrees, and apply it again at the same site for another 10 seconds. This will create 100 micropores at each site. Micropatch application will only occur on Day 0.

Immediately after treating a site with a micropatch, TEWL and impedance measurements will be repeated. The site will then be covered with a sterile occlusive cover, and the researcher will apply a new micropatch array to the next site. Two sites at each location will not receive micropatch treatment. An occlusive covering will be placed over one of these two sites, and the other untreated site will remain uncovered. The 4 covered sites will be secured with medical tape. Note that all baseline measurements, micropatch applications, Day 0 post-micropatch measurements, and covering and medical tape placement will be performed at one anatomical location (5 sites) before proceeding to the next location. Day 0 procedures will require 3 - 4.5 hours.

Subjects will be asked to return to the CRU every 24 hours for 3 days. On each day hydration, impedance, and color measurements will be repeated at all sites. New occlusive material will be applied on Days 1 - 2. On Day 3 (the final day), covering will be removed, but not replaced. Procedures on Days 1-3 will last 2 - 3 hours.

Within 3-4 days after the Day 3 visit (or the last completed visit if a participant decides to drop out early) a study team member will contact the subject via phone or email to determine if the subject is experiencing any redness or irritation at the treatment site. No long-term follow-up will be necessary. The overall time commitment for this study is 9 - 13.5 hours in one week, across 4 study days if consent is obtained on Day 0, or 5 study days if consent is obtained before Day 0; consent may occur any time prior to study procedures.

**VII.E.7** *Will you attempt to recontact subjects who are lost to follow-up?*  
No - those lost to followup will not be recontacted

**VII.E.9** *Will subjects be provided any compensation for participating in this study?*  
Yes

**VII.E.10** *Cash*  
No

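### For hydration and colour, the own-baseline test mixes microneedle and covering effects, and the occluded-control test leaves out Day 0 readings that are already collected (minor)

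*Combined protocol and SAP*

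**What the plan says.** Section XI.1 gives hydration and colour two comparisons. In the first, "each daily measurement will be compared to its baseline at that site". In the second, the reading is compared "as well as to its hydration control (untreated, occluded site), using paired t-tests". XI.1 does not say which of the two supports a conclusion about microneedles. The second comparison, as written, has no Day 0 term.

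Section VII.E.6 sets out the sites. At each location three of five sites are treated, and after treatment "The site will then be covered with a sterile occlusive cover". For the two untreated sites: "An occlusive covering will be placed over one of these two sites, and the other untreated site will remain uncovered". The readings needed for a baseline-adjusted contrast are planned: "Noninvasive baseline measurements will be taken at each of the 15 sites as follows", and on Days 1 to 3 "On each day hydration, impedance, and color measurements will be repeated at all sites".

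Neither measure is the primary endpoint. On impedance, XI.1 says "This micropore half-life will serve as the primary endpoint". On size, XI.2 says "Our calculation of subject number was based on what is feasible for a pilot study", with 10 subjects in each of five groups.

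**The concern.** A treated site is both punctured and covered, so its change from Day 0 reflects both. The plan expects covering to matter, since it names the covered untreated site as the control for hydration. With no lead test named, a change from own baseline could be read as a microneedle response when the covering produced it.

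The occluded-control test answers the right question but ignores the Day 0 readings at both sites. Two things follow. Some precision is given up in groups of 10. And if the treated and control sites already differed on Day 0, that difference passes straight into the result. The documents give no rule for which of the five sites is treated or serves as control (the answer on randomization in VII.E.1 concerns subjects), so balance is not assured by design.

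**Working it through.** **Inputs from the documents.** Two paired t-tests (XI.1); 3 treated, 1 covered untreated and 1 uncovered untreated site at each of 3 locations, so 15 sites, all read on Day 0 and daily (VII.E.6); 10 completers in each of 5 groups, so 50 (XI.2). The documents give no alpha, SD, correlation or effect size for hydration or colour, so there is no stated figure to reproduce.

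**Assumptions.** Two-sided alpha 0.05 and normal data. For the own-baseline test, SD means that of the within-site change. Elsewhere it means that of the treated-minus-control difference, equal at both times, and r is the correlation of that difference between Day 0 and follow-up, taken as 0.3, 0.5 and 0.7.

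**Step 1: what each contrast estimates.** Let m be the microneedle effect, c the covering effect and δ the mean treated-minus-control difference at Day 0.

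- Own baseline: m + c.
- Same-day control: m + δ.
- Control contrast adjusted for Day 0 and read at a Day 0 difference of zero: (m + δ) − rδ = m + (1 − r)δ.
- Difference in changes: m.

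**Step 2: own-baseline test with m = 0.** Noncentral t, n = 10, 9 df, noncentrality d√n.

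- c = 0.5 SD: 0.5 × √10 = 1.58, rejection 0.293.
- c = 1 SD: 3.16, rejection 0.803.

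**Step 3: same-day control test with m = 0.**

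- δ = 0: rejection 0.05. The test is valid.
- δ = 0.5 SD: 0.293 in a group of 10; over 50 subjects, 0.5 × √50 = 3.54 with 49 df gives 0.934.

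**Step 4: variance relative to the planned control test, with δ = 0.** With a separate intercept per group and one shared slope, the baseline spread has 50 − 5 = 45 df, and the ratio is (1 − r²)(1 + 1/43).

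- r = 0.3: 0.91 × 1.0233 = 0.93.
- r = 0.5: 0.75 × 1.0233 = 0.77.
- r = 0.7: 0.51 × 1.0233 = 0.52.
- Break-even: (1 − r²)(44/43) = 1, so r = √(1/44) = 0.15.
- Difference in changes: 2(1 − r) = 1.4, 1.0 and 0.6.

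**Step 5: power for a 1 SD effect in one group of 10, with δ = 0.**

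| Analysis | r = 0.3 | r = 0.5 | r = 0.7 |
|---|---|---|---|
| Planned control test (9 df) | 80% | 80% | 80% |
| Variance pooled over groups, no Day 0 term (45 df) | 87% | 87% | 87% |
| Shared-slope adjustment (44 df, simulated) | 89% | 94% | 99% |
| Difference in changes (9 df) | 66% | 80% | 95% |

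Pooling gives 87 − 80 = 7 of the 89 − 80 = 9 points at r = 0.3, and 7 of 14 at r = 0.5. Adjustment within a single group of 10 gives about 78% at r = 0.3, slightly below the planned 80%.

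**Step 6: false positives with δ = 0.5 SD and m = 0 (adjusted rows simulated).** The adjusted analysis still carries (1 − r) × 0.5 = 0.35, 0.25 and 0.15 SD.

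| Analysis | Per group of 10 (r = 0.3, 0.5, 0.7) | Over 50 (r = 0.3, 0.5, 0.7) |
|---|---|---|
| Planned control test | 29%, 29%, 29% | 93%, 93%, 93% |
| Shared slope, read at zero | 19%, 14%, 10% | 60%, 42%, 25% |
| Difference in changes | 5%, 5%, 5% | 5%, 5%, 5% |

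**The case against.** The strongest reply is that the valid comparison is already in the plan. The covered untreated site exists at every location to separate covering from microneedles, and XI.1 uses it. Nothing in XI.1 says that a change from own baseline will be called a microneedle effect. This stands: naming a lead test would on its own be a matter of missing detail.

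A second reply is that the purpose is descriptive. Section I.6 says hydration and colour serve to characterize skin by location and race, the hypothesis rests on impedance, and the study is a feasibility-sized pilot. This stands as a limit on weight. Section IX.2 does link these measures to the response to microneedles, so attribution still matters.

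A third reply is that the Day 0 point rests on an unshown premise. A reader might infer that the occluded-control test is biased. The documents do not support that: they do not show that sites within a location differ, and if positions vary without pattern across subjects, leaving out Day 0 mainly costs precision. Nor does XI.1 forbid using Day 0; it simply does not mention it.

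A reader might also credit Day 0 with the whole rise in power from 80% to 89%, 94% and 99%. Step 5 shows otherwise: at r = 0.3 most of the rise comes from pooling variance across groups.

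What survives is narrower. The contrast that isolates microneedles can be made more precise, and better protected, with readings the plan already collects.

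**Conclusion.** The point holds, and it is minor. The own-baseline test cannot separate microneedles from covering. Under an assumed covering shift of 0.5 SD of the within-site change it gives a significant result in 29% of groups of 10 with no microneedle effect, and in 80% at 1 SD. The occluded-control test is valid if sites do not differ systematically. Leaving out Day 0 costs it a modest amount of precision (variance ratio 0.93, 0.77 or 0.52 at r = 0.3, 0.5 or 0.7) and leaves it exposed to a Day 0 site difference if one exists. Every SD, correlation and offset here is an assumption.

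A reader might infer that the study's main result is at risk. It is not: micropore half-life is the primary endpoint, and no primary conclusion depends on these tests.

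**What to change.** Replace the hydration and colour sentence in XI.1 with:

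> Conclusions about microneedle effects on hydration and colour rest on the mean of the treated sites minus the occluded untreated site on each day, adjusted for the same difference at Day 0 and estimated at a Day 0 difference of zero (the model intercept). The model is fitted at each location with a separate intercept per group and one baseline slope shared by the groups. The difference in changes from Day 0 is reported alongside as a sensitivity analysis. Change from own baseline is descriptive.

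The intercept wording is essential. Read at the average baseline instead, a single-group model at a 0.5 SD offset gives false positives of 32%, 38% and 50% (r = 0.3, 0.5, 0.7) against 29% for the planned test.

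The lead analysis should not be chosen by first testing the mean Day 0 difference over all subjects. With a 0.5 SD offset in one group only, the overall mean offset is 0.5/5 = 0.1 SD. That test would detect it in about 10% of trials, leaving false-positive rates in that group of 18%, 13% and 9%.

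**Cost.** Analysis wording only; no extra visit, reading or subject. The downsides are:

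- The model assumes one slope and one residual variance across groups.
- The gain from Day 0 itself is small at low correlation, and is nil at about r = 0.15.
- Adjustment removes only about the fraction r of a persistent site offset, which is why the difference in changes is reported too.
- The difference in changes is noisier than the planned test below r = 0.5.
- XI.1 does not say whether the three treated sites are averaged; this wording settles that they are.

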## XII. Future Research

**XII.1** *Do you wish to keep any information about subjects involved with this research project so that members of the current research team may contact them in the future for your own research projects?*  
Yes

**XII.2** *Do you wish to keep any information about subjects involved with this research project so that [other researchers](#) may contact them for future research?*  
No

**XII.3** *List the data or information you will keep:*  
Name and contact information.

**XII.4** *Does this project involve storing any data, tissues or specimens for future research?*  
No
